Title:

The effect of conversion to once-daily Envarsus® on the neurologic toxicity burden in liver transplant recipients

Institution:

Medical University of South Carolina

Principal Investigators:

[name]

Office: [contact] [contact] Email: [contact]

1) Study Objectives

- a) Primary objective
 - i) Estimate the change from baseline to six months in neurotoxicity burden measured by a composite Patient Global Impression of Improvement (PGI-I) (Appendix B) score in patients converted to Envarsus daily ± adjunctive agent ± prednisone versus patients maintained on a standard therapy of Tacrolimus IR BID ± adjunctive agent ± prednisone

b) Secondary objectives

i) Estimate the change in the mean Fahn-Tolosa-Marin (FTM) score in patients with selfreported tremor from baseline to 6 months after enrollment

c) Exploratory Outcomes

- Examine subject specific change of self-reported adherence using the IMAB-Q 10 (Appendix C) at the time of the conversion versus six months post-conversion, compared between the two arms
- **ii)** Examine subject specific change in quality of life, using the SF-12 at the time of conversion versus six months post-conversion, compared between the two arms
- **iii)** Examine subject specific change in memory, using the Medical Symptom Validity Test, at the time of conversion versus six months post-conversion, compared between the two arms
- **iv)** Examine subject specific change in cognition, using the MoCA (Appendix E), at the time of conversion versus six months post-conversion, compared between the two arms
- v) Examine subject specific change in cognition, using the MMSE, at the time of conversion versus six months post-conversion, compared between the two arms
- vi) Measure and compare time-to-event analysis of secondary objective between the two arms
 - (1) Patient death (time to event analysis)
 - (2) Biopsy proven acute rejection (Banff RAI ≥ 5, time to event analysis)
 - (3) Graft loss (time to event analysis)
- vii) Compare rates of adverse events and severe adverse events between the two arms
- viii) Examine subject specific change in renal function, using the 4 variable MDRD, at the time of conversion versus six months post-conversion, compared between the two arms

2) Background

a) Rationale

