Diabetes	21 (43)	16 (15)				

ADRs in Multicenter Prospective, Randomized U.S. Trial

•		
	Tacrolimus	Cyclosporine/AZA
	(n=250)	(n=250)
Headache	64%	60%
Insomnia	64%	68%
Tremor	56%	46%
Paresthesia	40%	30%

3) Study interventions

- a) Interventions, administration, and duration
 - i) Subjects will receive the current standard of care for up to 15 days and no longer than 1 year post-transplant. Standard of care is described as a regimen of tacrolimus IR (goal 12 hour trough: 3-10ng/mL) BID ± adjunctive agent ± prednisone. Subjects are randomized to one of the two arms to either receive their standard of care regimen or convert their tacrolimus IR BID to Envarsus QD
 - (1) Both products FDA approved for preventing rejection in kidney transplant and are used as a standard of care for all organ transplants
 - ii) Post-randomization, subjects will be converted to one of the two arms, as shown below, and followed for a total period of six months (primary endpoint), or until a terminal end point is reached.
 - (1) Arm 1: Control-- Tacrolimus IR (goal 12 hour trough: 3-10ng/mL) BID ± adjunctive agent ± prednisone x 6 months
 - (2) Arm 2: Intervention-- Envarsus (goal 24 hour trough: 3-10 ng/mL) daily ± adjunctive agent ± prednisone x 6 months

- (a) Envarsus will be supplied from Veloxis Pharmaceuticals
- b) Neurotoxicity assessment
 - Changes in neurotoxicity comorbidity burden will be assessed at all study visits noted on the Schedule of Evaluations, using the composite score from applying the PGI-I score to tremor, headache, insomnia, and paresthesia.

4) Study Endpoints

- i) Primary outcome- Treatment efficacy, defined difference in change from baseline to six month measure by composite PGI-I in both arms.
- ii) Secondary outcomes
 - (a) Change in the FTM score in patients with self-reported tremor between baseline and six months post-enrollment in both arms
- iii) Exploratory outcomes
 - (1) Safety outcomes of treatment failure rate, defined as acute allograft rejection with a Banff RAI 5 or higher, graft loss, death, adverse events, or severe adverse events at six months post-conversion in both arms.
 - (2) Change in self-reported medication adherence, defined as the IMAB-Q10, between baseline and six months post-conversion in both arms
 - (3) Change in the subject specific quality of life, defined as the SF-12, between baseline and six months post-conversion in both arms

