 - (1) No deviations from or changes to the study protocol should be initiated except when necessary to eliminate immediate hazard to the subject. However, the IRB and Study Sponsor must be informed of this as soon as possible thereafter. It is the PI's responsibility to report SAEs occurring during the study to the IRB, as required and as soon as possible.

10) Study design

- i) Single-center, open-label, randomized comparative trial for a duration of 6 months.
- ii) There will be 15 subjects in each arm, with a total study size of 30 subjects.
- **b)** Allocation: Three random permuted-blocks of ten, with equal arm allocation ratio will be used. In each block, REDCap will be used to ensure 1:1 randomization, with resulting 1:1 allocation in the overall cohort.
- c) Intervention Model: Parallel assignment
- **d)** Masking: This will be an open-label study as masking is not feasible given we are comparing twice-a-day to once-a-day regimen.
- e) Timing of evaluation
 - i) Pre-Randomization Evaluations
 - 1. Baseline
 - Evaluations listed under the baseline visit may be performed up to 14 days prior to randomization. Once the subject has been successfully screened and accepted for randomization, randomization must be completed within 48 hours.
 - ii) Intervention and Evaluations
 - Once the subject has been successfully randomized, study medication will be picked up from IDS by the study team to be dispensed to the subject or study medication will be shipped to the subject by IDS. Study evaluations must take place within the time window indicated on the Schedule of Evaluations (Section 3)
- f) Clinical and laboratory evaluations

i) Schedule of evaluations

Data Collection Schedule

	Baseline	Baseline Days Post-Conversi					on			
Report Form			7±2	14±3	30±5	60±7	90±10	120±10	150±10	180±10
Informed Consen	t Obtained ^{vi}	Х								
Randomization		Х								
Review of Inclusion	on and Exclusion Criteria	Х								
Medical History		Х								
Liver Transplant F	Recipient	Х								
Review of Medica	ations and Dosing	Х								Х
Clinical assessment* Adverse events, rejection, graft loss, death						х			х	
	PGI-I, IMAB-Q 10, MSVT, MoCA, and SF- 12, MMSE ^v	х								х
	Fahn-Tolosa-Marin ^{iv}	Х								Х
Laboratory	CBC and Chem-7 ⁱ	0	0	0	0	0	0	0	0	0
Assessments	LFTs ⁱⁱ	0	0	0	0	0	0	0	0	0
	Tacrolimus CO ⁱⁱⁱ	0	0	0	0	0	0	0	0	0
End of Study										Х

X=required; 0=optional: data will be collected if performed as standard of care Footnotes:

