- i) Includes sodium, potassium, chloride, CO2, BUN, SrCr, glucose, calcium, WBC, HgB, Hct, platelets
- ii) Includes AST, ALT, alkaline phosphatase, total bilirubin, albumin, total protein
- iii) Tacrolimus concentrations will be 12- or 24-hour levels, drawn in the morning of each assessment
- iv) Only required for patients with self-reported tremor
- v) MSVT,MMSE, MoCA, FTM will be completed through a Doxy.me visit. PGI-I, IMAB-Q 10 and SF-10 will be sent to the subject through REDCap to be completed. Necessary materials (ball point pen and paper) to complete the MoCA, MMSE, and FTM will be shipped to the subject prior to the Doxy.me visit.
- vi) For subjects consented through Doxy.Me, this will be done prior to the baseline visit with the assessments.

11) Specimen Collection and Assessments

- i) Clinical and Laboratory Assessments:
 - (1) Laboratory evaluations will be performed at certified laboratories according to the study schedule. Required tests are specified in the Schedule of Evaluations. Laboratory

- specimens will not be stored for the study or sent to any outside facilities. Specimens will not be used for future research.
- (2) All subjects will undergo clinical assessment by the investigator or the investigator's designee in the manner and at the times specified in the Schedule of Evaluations
 - (a) Adverse events will be determined and defined according to the protocol
 - (b) Doses will be recorded of all immunosuppressants.
 - (c) Rejection and infection events will be recorded, as defined in the protocol
- (3) Renal function assessment will be monitored at regular intervals using the 4-variable abbreviated MDRD equation. It will be monitored at baseline and the end of the study for study outcomes and any time points dictated by standard of care follow-up in between those time points.
- ii) Definitions
 - (1) Acute rejection is defined as a liver allograft biopsy showing RAI 5 or greater, by the 1997 Banff Criteria and all updates since then. Biopsies will be performed when clinically warranted, based on changes in allograft function.
 - (2) Rejection reversal is defined as return of liver function tests to within 20% of baseline and/or histologic clearance by Banff Criteria
 - (3) Recurrent acute rejection is defined as rejection recurring more than two weeks after documented rejection reversal.
- iii) Treatment of Acute rejection:
 - (1) Acute rejection will be treated per provider discretion.
- iv) Opportunistic Infections

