 - (1) Opportunistic infections will be defined as outlined in Appendix F
- v) Intervention Discontinuation Evaluations: At the scheduled time of intervention discontinuation (EOT, last date of study), the following evaluations must be completed: clinical assessment, CBC, CHEM-7, LFTs, Tacrolimus CO. In case of subject withdrawal from study, the patient will return to standard of care medications and request to continue with final assessment using PGI-I, IMAB-Q 10, MSVT, MoCA, SF-12, MMSE, and FTM (if applicable) will be discussed with a qualified team member.

12) Data Management

- a) Data management will be overseen and data analysis will be independently reviewed by an Investigator on the study who has no related financial interest. This member will serve as independent monitor to oversee data collection and management, and to verify the integrity of data and interpretation of study results. Data reports, including patient recruitment and randomization numbers, clinical outcomes (acute rejections, infections and hospitalizations), AEs and SAEs will be reviewed quarterly.
- b) Dichotomous data will be analyzed using Chi Square or Fischer Exact, when appropriate, and continuous data points will be analyzed using Student's t-test or Mann Whitney U, for parametric and nonparametric data, respectively.
- c) Sample size estimation for the primary outcome
 - i) The proposed sample size (n=30) would be able to demonstrate a mean difference in neurologic toxicity burden, using the Patient Global Impression of Improvement (PGI-I) rating of 20 ± 15 with greater than 80% power using a two-tailed t-test with an alpha set at 0.05. Based on reported neurologic toxicities from the literature (headache 64%, insomnia 64%, tremor 56%, paresthesia 40%), a mean score of 45 is expected at baseline. Using the independent samples t-test comparing two groups with a two-sided significance level of

0.05, a sample size of 14 subjects per group would be required to obtain a power of at least 0.8 if the two groups have a mean of 25 ± 15 neurologic toxicity burden in the Envarsus cohort at the conclusion of the study and mean of 45 ± 20 neurologic toxicity burden at baseline and follow up in the tacrolimus IR group. Estimating a 10% drop out rate, we propose a sample size of 15 subjects per group. This sample size will provide adequate power to show a statistical and clinical difference in the neurologic toxicity burden between the two groups.

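### The only secondary objective (FTM tremor score) does not state a between-arm contrast or a baseline adjustment, so its wording also permits a before-after report

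*Combined protocol and SAP*

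**What the plan says.** Section 1(b)(i) gives the secondary objective: "Estimate the change in the mean Fahn-Tolosa-Marin (FTM) score in patients with selfreported tremor from baseline to 6 months after enrollment". Section 4(ii)(a) gives the endpoint: "Change in the FTM score in patients with self-reported tremor between baseline and six months post-enrollment in both arms". Neither sentence asks for a difference or a comparison.

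The neighbouring text does. The primary objective sets Envarsus against tacrolimus IR, and its endpoint in section 4(i) is a "defined difference in change from baseline to six month measure by composite PGI-I in both arms". The exploratory objectives on quality of life, memory, cognition and renal function end "at the time of conversion versus six months post-conversion, compared between the two arms", and the one on adherence is to the same effect. The items on death, rejection, graft loss and adverse events also call for a comparison of the arms.

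The only general analysis text, section 12(b), assigns continuous data to Student's "t-test or Mann Whitney U, for parametric and nonparametric data, respectively". It does not mention FTM, a baseline adjustment or an interval estimate. Section 10 describes a "Single-center, open-label, randomized comparative trial for a duration of 6 months", "with resulting 1:1 allocation in the overall cohort". Footnote iv to the schedule of evaluations says of the FTM: "Only required for patients with self-reported tremor". It does not say at which visit tremor status is judged.

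**The concern.** An analyst who follows section 1(b)(i) to the letter could report the mean FTM change within the Envarsus arm, in each arm separately, or over both arms together. None of these isolates the effect of conversion. Patients who report tremor may on average be at a high point when first measured, and those enrolled soon after transplant may improve on either product. Both effects would appear as a fall in FTM with no drug effect. The difference between randomised arms removes them in expectation, because they act on both arms alike.

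This matters because the trial is open-label with a self-reported primary outcome. FTM is the examiner-rated measure of one of the four symptoms in the primary composite, so a reader will look to it for support.

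There is also a smaller gap in method. The section 12(b) tests make no adjustment for baseline FTM, although it is already collected. With so few patients, chance imbalance at baseline will not be negligible.

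**Working it through.** **Plan's own figure.** The documents give no effect size, SD or power for FTM. As a check on method, the primary calculation (means 25 and 45, SDs 15 and 20, two-sided alpha 0.05) has pooled SD √((15² + 20²)/2) = 17.68. The noncentral t gives power 0.790 at 13 per arm and 0.822 at 14, so the stated 14 per group reproduces. The same method is used below for FTM.

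**Size of the FTM subset.** Section 12(c) uses a tremor rate of 56%. 0.56 × 15 = 8.4 per arm, or 8.4 × 0.9 = 7.6 after the planned 10% dropout; take 8.

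**Fall expected with no drug effect.** Suppose the subset is the top 56% on a normal variable S that correlates ρ₀ with baseline FTM and ρ₁ with six-month FTM. The mean of S in the subset is φ(−0.151)/0.56 = 0.704, so the expected fall is 0.704 × (ρ₀ − ρ₁), in cohort SDs of FTM.
- If selection is on measured baseline FTM itself, ρ₀ = 1 and ρ₁ is the retest correlation r. The fall is 0.704 × (1 − r).
- If self-report correlates equally with FTM at both visits, ρ₀ = ρ₁ and the fall is zero.

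| Assumed r | Fall if selected on baseline FTM |
|---|---|
| 0.9 | 0.07 SD |
| 0.8 | 0.14 SD |
| 0.7 | 0.21 SD |
| 0.6 | 0.28 SD |

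The plan selects on self-report, so the table is close to an upper limit for regression to the mean. Every r is assumed.

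**How often each analysis is significant with no drug effect.** This is a simulation of 20,000 trials per setting with 8 per arm, normal FTM and the same worst-case selection. The 0.3 SD recovery is an assumption.

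| r | Recovery | Within one arm | Both arms pooled | Between-arm t-test of change |
|---|---|---|---|---|
| 0.5 | 0 | 15.6% | 29.3% | 5.2% |
| 0.7 | 0 | 10.4% | 18.6% | 4.9% |
| 0.9 | 0 | 6.6% | 8.8% | 4.9% |
| 0.5 | 0.3 SD | 40.2% | 75.5% | 4.9% |
| 0.7 | 0.3 SD | 38.8% | 73.3% | 4.9% |
| 0.9 | 0.3 SD | 53.9% | 88.1% | 5.1% |

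Only the between-arm test holds its 5% level throughout.

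**Why adjust for baseline.** With 8 per arm, the chance difference in mean baseline FTM has standard error √(2/8) = 0.5 SD. If the variance is equal at both visits, a baseline difference of 0.5 SD shifts the unadjusted difference in change by (1 − r) × 0.5, which is 0.05 SD at r = 0.9 and 0.20 SD at r = 0.6. ANCOVA removes this shift.

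**What the comparison can show.** With 8 per arm, 80% power needs a between-arm difference of 1.51 SD of the change score. Over an assumed range of tremor rates, 42% (6 per arm) needs 1.8 SD and 75% (10 to 11 per arm) needs about 1.3 SD.

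**The case against.** The best defence is the drafting pattern. The endpoints in section 4 for adherence, quality of life, memory, cognition (MoCA) and renal function follow the same template as the FTM endpoint: a change, measured in each arm, with no mention of a difference. Their objectives in section 1 show that this template means a between-arm comparison. Section 12(b) points the same way, since Mann-Whitney is a two-sample test and no paired or one-sample test is named anywhere. The background hypothesis is also comparative. On this view, one phrase is missing from one objective.

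Much of this stands, and a reader should not infer that the plan commits to a before-after analysis or to discarding its control arm. The defence does not fully close the gap. For the other outcomes the objective supplies the comparison that the endpoint leaves out; for FTM neither does. Section 12(b) names Student's t-test without saying paired or independent, and the independent-samples wording appears only in the primary sample-size text.

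Two further inferences are tempting and unsupported. FTM is not the only examiner-scored outcome: MoCA and MMSE are too, and both are compared between arms. Nor is the trial enriched for tremor: it is not an entry criterion in section 5, and only the FTM subset is defined by it.

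**Conclusion.** The point holds as a gap in specification. The objective and endpoint do not state the FTM contrast, and no text sets an adjusted estimate for it. A between-arm comparison is the likely intent, but the wording also permits a before-after report, which could present regression to the mean or recovery as a drug effect. That it would do so does not follow from the documents.

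The size cannot be derived from the plan. The range of 0.07 to 0.28 SD rests on normality, on selection by baseline FTM itself and on assumed retest correlations of 0.9 to 0.6; selection by self-report could bring it near zero. Natural recovery would add to it by an amount the documents do not give. The simulated error rates carry the same assumptions.

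**What to change.** Restate sections 1(b)(i) and 4(ii)(a) as: *Between-arm difference (Envarsus minus tacrolimus IR) in change in FTM score from baseline to day 180 among patients with self-reported tremor at baseline, estimated by ANCOVA adjusting for baseline FTM, with 95% CI.* Add that within-arm changes are descriptive only and support no efficacy claim, and that the comparison is for estimation.

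Amend footnote iv so that tremor status is fixed at baseline and everyone in that group has the day-180 FTM, even if the tremor has resolved. If status were judged afresh at day 180, the subset would depend on response to treatment.

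The cost is a few sentences; FTM is already scheduled at baseline and day 180. ANCOVA uses one degree of freedom (14 to 13 with 8 per arm). The interval will be wider than for a before-after change: for the same SD of change, the standard error of the unadjusted difference is √2 = 1.41 times that of one arm's mean change, and twice that of the pooled change over 16 patients.

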 - (4) Change in subject specific memory, defined as the MSVT, between baseline and six months post-conversion in both arms
 - (5) Change in subject specific cognitive function, defined as the MoCA, between baseline and six months post-conversion in both arms
 - **(6)** Change in subject specific renal function, defined as the 4 variable MDRD, between baseline and six months post-conversion in both arms

5) Inclusion & Exclusion Criteria

- i) Potentially eligible patients will be screened by the PI and study coordinator using inclusion and exclusion criteria below to determine if they qualify for the study.
- ii) Inclusion criteria
 - (1) Male or female adult (≥18 years old) with a history of liver or liver/kidney transplant within 15 days to 12 months of transplant.
 - (2) Patients must be capable of understanding the purposes and risks of the study and have the ability to give written informed consent and be willing to participate and comply with the study. For those that consent virtually, subjects must be willing and able to use the Doxy.me platform and complete assessments virtually.
- iii) Exclusion criteria
 - (1) Patients will be excluded if they are pregnant or nursing females or males with a pregnant female partner
 - (2) HIV positive (HIV ab +)
 - (3) Unable to tolerate oral medications
 - (4) Use of another investigational product within thirty days prior to receiving study medication
 - (5) Moderate acute cellular rejection (RAI ≥ 5) within the past month
 - **(6)** A condition that is known to cause tremor such as essential tremor, Parkinson disease, or enhanced physiologic tremor.
 - (7) Patients taking medications known to induce tremors or dopamine blocking agents

(8) A condition or disorder that, in the opinion of the investigator, may adversely affect the outcome of the study or the safety of the subject

6) Number of Subjects

a) There will be 15 subjects in each arm, 30 subjects total

7) Setting Where Research Will Be Conducted

a) Study activities, including consent, enrollment, and randomization, will occur in the Liver Transplant Clinic at the Medical University of South Carolina or through Doxy.me.

8) Recruitment Methods

- a) Study enrollment procedures

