 - i) Subject Identification/Recruitment: Members of the research team will identify potentially eligible patients who have undergone liver or liver/kidney transplantation within the past twelve months. An initial evaluation of existing patient information may be performed via chart review to determine potential eligibility. This initial review may be performed prior to consent; however no protocol driven tests or procedures may be performed until signed informed consent has been obtained.
 - ii) Informed Consent: A qualified member of the research team, Human Subjects Protection Trained, will approach and explain the study and offer participation. The study will be explained in a manner consistent with the level of education pertaining to the patient. Enrollment procedure will involve face-to-face meetings of the patients to inform and review informed consent documentation. The participant will sign the consent form prior to evaluation of self-reported measures. Copies of the informed consent will be appropriately placed in the corresponding chart and the patient will be provided with a copy of the signed consent form. Non-consenting individuals will also be ensured that no penalty will arise due to denying participation. Those who choose to participate in the trial will be informed that at any point they reserve the right to leave the study.
 - iii) Enrollment: Patients who give informed consent to study participation will go on to complete baseline procedures necessary to determine eligibility for randomization. Once deemed eligible for the study according to the inclusion/exclusion criteria, the patient will be enrolled as study participant. Information to be entered upon enrollment includes demographic information and date of transplant surgery. Enrolled subjects will be randomized to one of the treatment arms in the applicable cohort.

9) Consent Process

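### The exploratory eGFR comparison pools liver-alone and liver/kidney recipients without adjusting for transplant type or baseline eGFR; it is valid on average but loses precision and is exposed to an uneven split

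*Combined protocol and SAP*

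**What the plan says.** - **Outcome.** Section 4 iii) (6): "Change in subject specific renal function, defined as the 4 variable MDRD, between baseline and six months post-conversion in both arms". Objective 1 c) viii) makes it a between-arm comparison: "change in renal function, using the 4 variable MDRD, at the time of conversion versus six months post-conversion, compared between the two arms".
- **Population.** Section 5 ii) (1) admits adults "with a history of liver or liver/kidney transplant within 15 days to 12 months of transplant". No cap or quota is set for either type.
- **Timing.** Section 11 i) (3), on MDRD eGFR: "It will be monitored at baseline and the end of the study for study outcomes". A baseline value is therefore planned.
- **Allocation.** Section 10 b): "Three random permuted-blocks of ten, with equal arm allocation ratio will be used". No stratification factor is named. Sections 8 a) iii) and 9 b) add: "Enrolled subjects will be randomized to one of the treatment arms in the applicable cohort". The cohort is not defined there, and section 10 b) speaks of one overall cohort.
- **Analysis.** Section 12 b): "continuous data points will be analyzed using Student's t-test or Mann Whitney U, for parametric and nonparametric data, respectively". No covariate, stratum, subgroup or sensitivity analysis is named for any continuous outcome.

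**The concern.** In a liver-alone recipient, eGFR reflects the native kidneys. In a liver/kidney recipient it also reflects a kidney graft, which may be as little as 15 days old at entry. A change score removes a stable difference in level between the two types, but not a difference in their six-month course. With 15 patients per arm, a few patients on a different course can move an arm mean.

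The planned test also makes no use of two baseline facts: the baseline eGFR, and the transplant type, which must be known to apply the entry criterion. At stake is how the renal result reads. A between-arm difference could partly reflect case mix, or a real one could be blurred, and section 15 d) lists kidney injury among the risks.

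**Working it through.** **1. The plan's own figure.** The only sample size calculation, section 12 c), is for the PGI-I composite. With means 45 and 25 and SDs 20 and 15, the pooled SD is √((15² + 20²)/2) = 17.68. A two-sided t-test at 0.05 then has power 0.790 with 13 per group and 0.822 with 14, so the stated 14 per group reproduces. The plan gives no effect, SD or power for eGFR.

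**2. Inputs for eGFR.** From the documents: 15 per arm, 1:1 allocation, blocks of ten, unadjusted test. Assumed, because the documents give nothing: K liver/kidney recipients among 30 (K = 3 as the main case, 2 to 6 as the range); within-type SD of change 15 mL/min; a gap g of 0 to 40 mL/min in mean six-month change between types; a true arm effect of 10 mL/min; two-sided 0.05, which the plan states only for the primary outcome.

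**3. Chance of an uneven split.** For K = 3, P(all in one arm) = 2·C(15,3)/C(30,3) = 2 × 455/4060 = 0.224. Simulating three blocks of ten gives 0.226. For K = 2, both fall in one arm with probability 48%. For K = 4, all four do with probability 10%. For K = 6, a 5-1 split or worse has probability 17%.

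**4. Shift given the split.** The unadjusted difference moves by g × (excess in one arm)/15. With all three in one arm this is 3g/15: 2 mL/min at g = 10, 4 at g = 20, 8 at g = 40.

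**5. Error rate.** Over all randomisations with no drug effect, the unadjusted t-test rejects in 4.8% to 5.2% of simulated trials. Restricted to trials where K = 4 and all four fall in one arm, it rejects in about 7% at g = 10 and 18% at g = 30. With a type term the rate is about 5%.

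**6. Precision at K = 3 (p = 0.1).** SD inflation = √(1 + g²·p(1−p)·(30/29)/15²). At g = 20 this is √(1 + 400 × 0.09 × 1.0345/225) = √1.166 = 1.08. The equivalent sample loss is 1 − 1/1.166 = 14%. Power is from simulation with 4,000 to 6,000 trials per setting, so differences of about 0.01 are noise.

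| Gap g (mL/min) | SD inflation | Sample loss | Power, unadjusted | Power, with type term |
|---|---|---|---|---|
| 0 | 0% | 0% | 0.43 | 0.42 |
| 10 | 2% | 4% | 0.41 | 0.41 |
| 20 | 8% | 14% | 0.38 | 0.41–0.42 |
| 30 | 17% | 27% | 0.31–0.33 | 0.41–0.42 |
| 40 | 29% | 40% | 0.28 | 0.42 |

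The type term therefore gains nothing visible up to g = 10, and from 0.41 − 0.38 = 0.03 to 0.42 − 0.28 = 0.14 between g = 20 and g = 40.

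**7. Adding baseline eGFR.** Suppose the two visits have equal variance σ² and within-type correlation ρ. The change score has variance 2σ²(1 − ρ), and the residual after regression on baseline has σ²(1 − ρ²). The ratio is (1 + ρ)/2: 0.80 at ρ = 0.6 and 0.90 at ρ = 0.8. An SD of 15 becomes 15√0.80 = 13.4 or 15√0.90 = 14.2. Simulating the full model (arm, baseline eGFR, type) with ρ of 0.6 to 0.8 gives power of about 0.41 to 0.49, against 0.28 to 0.44 unadjusted. It was never materially worse, and both methods stayed near 5% error.

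**The case against.** The strongest reply is that randomisation already deals with chance imbalance: the unadjusted comparison is unbiased and its standard error allows for uneven splits. This stands, and step 5 confirms it. A reader might infer that the planned test produces false renal findings more often than 5%. It does not. The bias exists only conditionally on the split that occurs, and only if the six-month change differs by type.

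Second, the size rests on inputs that the documents do not supply. A reader might infer a large gap from the possibility of a 15-day-old graft. But entry runs to 12 months, nothing shows that liver/kidney recipients will enter early, and no figure for their change is given. At a gap of 10 mL/min or less the type term earns nothing. If no liver/kidney recipient enrols, that part of the point disappears, though the gain from baseline eGFR remains.

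Third, a reader might take eGFR to be the trial's only view of the kidney. It is not. Adverse event rates are compared between arms (objective 1 c) vii), and section 13 b) counts clinically significant laboratory abnormalities as adverse events, graded by CTCAE.

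Fourth, other factors, such as time since transplant, could be prognostic too, and no document ranks transplant type first. That is fair. The case for it is that it changes which kidneys the outcome measures and is already an entry item.

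Finally, the reference to an applicable cohort might be read as stratification. It is undefined, and section 10 describes a single cohort, so it cannot carry that meaning.

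**Conclusion.** The point holds as one of efficiency and of conditional bias, not of invalidity. The planned eGFR comparison is sound on average but leaves precision unused, and an uneven split of liver/kidney recipients would make its result hard to read. Under the assumptions in step 2, the type term is worth nothing to about 0.14 of power, depending on a gap that the documents do not give. Baseline eGFR adds a gain that depends on its correlation with the six-month value. Even the better model reaches power of only about 0.41 to 0.49 for 10 mL/min, so the comparison stays exploratory in fact as well as in name. This is a cheap improvement of low consequence; the primary and secondary outcomes are unaffected.

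**What to change.** In section 12 b), state that six-month MDRD eGFR will be analysed by a linear model with arm, baseline eGFR and transplant type (liver v liver/kidney). Show the liver-alone result as a sensitivity analysis, and report the number of liver/kidney recipients in each arm. Naming the covariates now avoids choosing them after an imbalance has been seen.

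The cost is a sentence or two and no new data, since the change score needs the same two eGFR values. Against the t-test, the model uses two more degrees of freedom, and its type coefficient would rest on a handful of patients, so that coefficient should not be interpreted. If the types do not differ, the type term costs about 0.01 to 0.02 of power.
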